7.2.2 Clinical Experience

Prior Experience in Patients with Intracerebral Tumors

The occurrence of human DCs in the peripheral blood is low (0.15% of circulating mononuclear cells), and procedures to isolate circulating DCs are cumbersome, relying on negative selection techniques to deplete the mononuclear cell fraction of contaminating monocytes and lymphocytes. Furthermore, brain tumor patients are characteristically immunosuppressed either from the use of steroids or due to the fact that malignant brain tumors secrete immunosuppressive agents like TGF- β . We have been using a simple method described

previously[117], to generate human DCs by culturing PBMCs in media supplemented with GM-CSF and IL-4. We have compared the ability to generate DCs from patients with malignant brain tumors and patients undergoing craniotomy for non-tumor related procedures. The phenotype of DCs from both tumor and normal populations were identical and were characterized as being highly positive for HLA-ABC and HLA-DR, the co-stimulatory molecules CD80 and CD86, and the DC/monocyte marker CD11c, but negative for the monocyte marker CD14. The cells were negative for the B and natural killer (NK) cell lineage markers, CD19 and CD56, respectively, which is consistent with published DC phenotypes.

DC immunotherapy in patients with MGs has been evaluated only a few studies. In the published study by Yu *et al.* [118], patients received biweekly intradermal injections of peripheral blood derived DCs pulsed with uncharacterized peptides eluted from the surface of autologous glioma cells by gentle acid washings. All patients were required to complete a course of RT and were off steroids at the time of immunization. Toxicity was minimal and included only mild fever and lymphadenopathy. There was no clinical or radiographic evidence of autoimmune encephalomyelitis in any patient and no serious adverse events occurred. The immunization resulted in enhanced CTL activity in 4/7 patients and both cytotoxic and memory T cells were found to have infiltrated the patient's tumors whom underwent reoperation after immunization. Although this study was performed in a selected population of patients, the median survival of 455 days in the treated group compared very favorably with an institutional control group where median survival was only 257 days. Similarly, when immunized patients were compared to expected outcome per Curran's recursive partition analysis, which controls for known prognostic factors (Karnofsky Performance Status, histology, surgery, mental status, etc), the results still appeared quite favorable. Unfortunately, no clinical responses were seen and any antigen-specific immune response could not be characterized because the immunizing antigens were not characterized.

A study by Kikuchi *et al.* (2001) [119] used autologous DCs fused with autologous tumor cells as an immunogen in an 8 patient trial. The immunization schedule consisted of 3 to 7 vaccinations 3 weeks apart given intradermally. All vaccinations were well tolerated.

In another Phase I/II trial, tumor lysate pulsed DCs were given to ten patients who received immunizations every three weeks for a minimum of one and a maximum of 10 immunizations. There were only two minor clinical responses seen. Of five patients evaluated by ELISPOT before and after vaccination T cells reactive against tumor lysate-pulsed DCs were increased in two patients[120]. In a more recently published study, patients with GBM were treated with 1×10^6 to 1×10^7 DCs pulsed with acid eluted autologous tumor peptides[121]. There was no evidence of DLT or serious adverse events. One patient had an objective clinical response documented by magnetic resonance imaging, and six patients developed measurable systemic antitumor CTL responses.

In a more recent study, Kikuchi *et al.*[122] investigated the safety and clinical response to immunotherapy using fusions of DCs and glioma cells combined with recombinant human IL-12 for the treatment of MG. Fifteen patients with MG participated in this study. Cultured autologous glioma cells were established from surgical specimens in each case. Fusion cells were prepared from DCs and glioma cells using polyethylene glycol. All patients received fusion cells intradermally on day 1. IL-12 was injected subcutaneously at the same site on days 3 and 7. No

serious adverse effects were observed. In four patients, magnetic resonance imaging showed a greater than 50% reduction in tumor size. One patient had a mixed response. In our ongoing Phase I/II clinical trial (BB IND 9944) patients with newly-diagnosed MGs are vaccinated with mature DCs loaded with a peptide spanning the fusion junction of EGFRvIII conjugated to keyhole limpet hemocyanin (PEPvIII-KLH) (500 mcg/immunization), mixed with GM-CSF (approx. 150 mcg/immunization). EGFRvIII is a tumor specific antigen, which is expressed on approximately 47% of all MGs. The vaccination protocol consists of 3 vaccines 2 weeks apart of PEPvIII-KLH loaded, mature DCs beginning 2 weeks following completion of post-resection RT. To date, 19 patients have been enrolled with 16 completing vaccination with no adverse events. No patient showed a positive delayed-type hypersensitivity reaction to KLH or PEPvIII before vaccination and of the evaluable patients after vaccination, 14/15 (93.3%) patients reacted to KLH and 11/15 (73.3%) reacted to PEPvIII. *In vitro* proliferation in response to PEPvIII was seen in 11/12 (92%) and to KLH in 9/12 (75%) of patients tested. Two patients, one with anaplastic astrocytoma and one with GBM with residual radiographic disease after resection, and

[figure not shown]

Figure 4. Patient from prior vaccination study with a nearly complete response. Progressive MG after radiation and temozolomide (top) with nearly complete response, 3 months after PEPvIII-pulsed DC vaccine (bottom).

[figure not shown]

Figure 5. TTP comparison between VICTORI Trial, ACTIVATE Trial, and a historical control. TTP comparison in patients treated with PEPvIII-KLH loaded DCs (VICTORI Trial), patients treated with PEPvIII-KLH alone (ACTIVATE Trial), and a historical control group that had a 95% resection of an EGFRvIII-positive tumor. There

was no significant difference in the TTP between the patients in the VICTORI and ACTIVATE trials, but both were significantly better than historical controls ($P < 0.001$).

radiation, have had a nearly complete response in our prior vaccination study which also included the use of chemotherapy agents such as TMZ (Figure 4). These patients have remained stable for 174.9 and 217.3 weeks. Of the 14 patients without radiographically evident disease, 4/14 (28.6%) have not progressed at 102.7, 171.3, 180.7, 430.7 weeks with a median overall time to progression of 10.4 months comparing favorably with a historical unvaccinated cohort (EGFRvIII positive and gross total resection) that had a median TTP of 7.1 months ($n=39$). (Figure 5) For patients with GBM, the median survival time was 20.0 months which compares favorably with recently published trials evaluating newly-diagnosed patients with GBM treated with GLIADEL®(13.9 months)[1]; radiation and concurrent TMZ (14.6 months)[2]; or radiolabeled anti-tenascin monoclonal antibodies performed at Duke University (18.3 months)[123] (Figure 7). This Phase I study has been completed. No toxicity has been seen (Figure 6). PBMC were isolated and analyzed by flow cytometry. $CD4^+$ is shown as percent of lymphocytes and T_{REGs} are shown as percent of $CD4^+$. T_{REGs} defined as $CD4^+CD25^+Foxp3^+$. Based on these results, the dose for this study will be 20 mg.

[figure not shown]

Figure 6. Basiliximab reduces TREGs in patients with GBM receiving DC vaccination. (B=Basiliximab, V=vaccine)

[figure not shown]

Figure 7. Survival comparison of patients with GBM treated with PEPvIII-KLH loaded DCs (VICTORI Trial) with patients treated at Duke University with 81C6 anti-tenascin ¹³¹I labeled MAb. Both patient populations had similar eligibility criteria. Published median survival for such patients treated with Gliadel™ is 59.6 weeks [1] and with concurrent RT and temozolomide is 58.4 weeks [2]

7.3 Study Purpose/Rationale

We have demonstrated in murine models that DCs loaded with tumor-specific antigens in the form of mRNA can induce potent and specific humoral and cell-mediated immune responses that are effective against murine i.c. tumors, including a syngeneic murine astrocytoma, without inducing autoimmunity [101, 104, 124]. Our previous clinical experience has also shown that DC vaccines in combination with standard of care radiation therapy and chemotherapy are capable of generating potent, tumor-specific immune responses and clinical radiographic responses in patients with MGs. We and others have also shown that antigens derived from *CMV* are contained within MGs and may serve as potent and specific immunotherapy targets. Vaccination and adoptive T cell strategies targeting *CMV* in humans in other contexts, including the targeting of lesions within the CNS, have been safe and effective. We have also shown that DCs generated from patients with GBM and loaded with pp65-LAMP mRNA are capable of generating CD4+ and CD8+ T cells that produce IFN- γ and kill malignant astrocytes infected with *CMV* in an antigen-specific fashion. We have found that TILs isolated from these patients are significantly enriched for T cells that specifically recognize *CMV* antigens, suggesting that this response may be important in the biology of these tumors.

CMV antigens have been identified in GBM and may make excellent antitumor immunotherapeutic targets. Vaccination and adoptive T cell strategies targeting *CMV* in humans in other contexts have been safe and effective. DC vaccinations targeting other antigens in GBM have been safe and effective. Other peptide vaccines given to patients with GBM during recovery from TMZ-induced lymphopenia have produced potent tumor-specific immune responses. TMZ has recently shown modest efficacy, but is not curative, in some patients with newly-diagnosed GBM and is now frequently given to these patients during and after RT. Preclinical studies demonstrate that vaccine responses are enhanced during the recovery from TMZ-induced lymphopenia, but a preferential recovery of immunosuppressive T_{Regs} during this homeostatic event likely serves to limit tumor-antigen directed immune responses. Preclinical studies have shown that unarmed antibodies specific for the high affinity IL-2 receptor constitutively expressed on T_{Regs} abrogate their immunosuppressive phenotype and indirectly enhance effector T cell responsiveness. This is consistent with the notion that the only non-

redundant function of IL-2 at physiologic levels is the maintenance of T_{Regs}. This may be especially true within the context of recovery from lymphodepletion when high levels of homeostatic cytokines such as IL-7 and IL-15 may drive activated T cell division in the absence of IL-2. Basiliximab a chimeric (murine/human) monoclonal antibody (IgG_{1K}), produced by recombinant DNA technology, functions as an immunosuppressive agent, specifically binding to and blocking the interleukin-2 receptor α -chain (IL-2R α , also known as CD25 antigen) on the surface of activated T-lymphocytes that may abrogate the functional recovery of T_{Regs} in patients with GBM recovering from TMZ-induced lymphopenia and enhance tumor-specific immune responses.

DC vaccines have shown considerable promise in the treatment of cancer. However, generally <5% of injected DCs actually reach the vaccine-site draining lymph nodes, limiting the induction of anti-tumor immune responses. We conducted a clinical trial with newly-diagnosed GBM patients who were randomized to pre-immunization with Td toxoid or unpulsed DCs before vaccination with *CMV* pp65 RNA-pulsed DCs (*ATTAC Trial*: FDA-IND-BB-12839). Strikingly, Td-treated patients had systemically enhanced DC migration and significantly improved PFS and OS compared to controls (PFS >36.6 vs 4.4 months, OS >36.6 vs 11.6 months). Our murine studies corroborated that Td pretreatment systemically enhanced DC migration and suppressed tumor growth. In the proposed clinical study, we aim to: 1) enhance the migration of *CMV* pp65 RNA-pulsed DCs with Td, and 2) to evaluate the effect of basiliximab and Td on survival outcomes when combined with DCs.

8 OBJECTIVES AND ENDPOINTS

Table 1. Objectives and Endpoints

	Objective	Endpoint	Analysis
Key Primary	To examine the impact of Td pre-conditioning with or without basiliximab on survival	Median survival from randomization	See Section 15.5.1
Other Primary	To determine whether pre-conditioning of the vaccine site with Td toxoid systemically increases the migration of CMV pp65 RNA-pulsed DCs to site-draining inguinal lymph nodes	The percentage of ¹¹¹ In-labeled DCs reaching inguinal nodes will be calculated from the initial signal at the injection site in the groin to 48 hours after the 4 th vaccination	See Section 15.5.2
Other Primary	To examine the impact to Td pre-conditioning on survival among patients who are CMV positive	Median survival from randomization	See Section 15.5.3
Other Primary	To assess the impact of Td pre-conditioning on survival among patients who are CMV negative	Median survival from randomization	See Section 15.5.4
Key Secondary	To examine the impact of Td pre-conditioning with and without basiliximab on progression-free survival	Median progression-free survival from randomization	See Section 15.6.1
Other Secondary	To examine the impact of Td pre-conditioning at the vaccine site on progression-free survival among patients who are CMV positive	Median progression-free survival from randomization	See Section 15.6.2
Other Secondary	To examine the impact of Td pre-conditioning on progression-free survival among patients who are CMV negative	Median progression-free survival from randomization	See Section 15.6.3
Exploratory	To describe changes from baseline in immune response as measured by IFN γ ELISpot	Median change from baseline in ELISpot at each follow-up assessment	See Section 15.7
Exploratory	To assess T cell polyfunctionality when ELISpot results are positive	Proportion of patients with 1, 2 and 3 functions at each assessment	See Section 15.7
Exploratory	To describe changes in T _{Regs} over time	Median change from baseline in T _{Reg} levels at each follow-up assessment	See Section 15.7
Exploratory	To measure levels of CCL3 and other inflammatory soluble factors	Median change from baseline in CCL3 and other inflammatory soluble factors.	See Section 15.7

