Our data from the ATTAC clinical trial (Duke IRB Protocol # Pro00003877) demonstrating the capacity to enhance DC migration to VDLNs via Td pre-conditioning of the vaccine site offer potential therapeutic interventions whereby we can enhance the immunologic responses to ultimately overcome the inherent challenges in faithfully eradicating established tumors. In a completed randomized clinical trial, we found that migration of injected DCs to VDLNs following vaccine site pre-conditioning with Td toxoid was significantly increased compared to controls and that the efficiency of DC migration was strongly associated with clinical outcomes of patients with newly-diagnosed GBM, the most fatal type of malignant brain tumors. To address this observation, we took our Td pre-conditioning platform back into the preclinical setting using transgenic mouse models and were able to corroborate the effects of Td pre-conditioning on increasing the lymph node homing of intradermally administered DCs. Moreover, Td administration at a single vaccine site increases the migration of a bilateral DC vaccine to both inguinal lymph nodes. Regardless of the side of the Td intradermal skin prep, DC migration to bilateral inguinal VDLNs was equally increased, supporting a systemic response to recruit peripherally administered DCs.

Our Td pre-conditioning platform in the context of DC vaccination also elicited superior anti-tumor responses compared to controls receiving DC vaccines without Td pre-conditioning. In our clinical trial, patients with newly-diagnosed GBM who were administered the Td skin prep before DC vaccination revealed significantly longer progression-free and overall survival rates compared to the control cohort. In evaluating the relationship between DC migration and clinical

responses, we observed a modest positive correlation between levels of DC migration and survival. In our preclinical model, Td pre-conditioning prior to vaccination with tumor antigen-specific DCs dramatically suppressed the growth of established and highly aggressive B16-F10/OVA tumors. The use of Td with a DC vaccine increased antitumor responses in an antigen-specific manner, as non-specific DC vaccines were not potentiated with Td pre-conditioning. Furthermore, in a challenge setting, where mice are administered the treatment platform prior to challenge with tumor inoculation, Td pre-conditioning at the vaccine site induced a significant survival benefit compared to controls.

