All enrolled patients will undergo a leukapheresis after resection for harvest of PBLs for generation of DCs. Patients will then receive approximately 6 weeks of standard of care RT and concurrent TMZ at a standard targeted dose of 75 mg/m²/d (please see Package Insert uploaded in eIRB for standard therapy). Patients should start RT within approximately 6 weeks of surgery. Patients who either experience progressive disease during radiation, are dependent on steroid supplements above physiologic levels at time of first vaccination, are unable to tolerate TMZ, or whose DCs or PBLs fail to meet release criteria will be withdrawn from the study and replaced and will not undergo repeat leukapheresis. For patients whose initial leukapheresis yields less than 3 vaccines, repeat leukapheresis may be obtained a minimum of 2 weeks from the previous leukapheresis (and may be repeated as needed) if pre-pheresis blood work is within the Apheresis Center's parameters and as long as this does not cause a significant delay in treatment for the patient. At the post-RT clinic visit where patient's MRI and blood work is evaluated prior to ordering the first post-RT cycle of TMZ, patients will be randomized to receive DC vaccination with one of three treating regimens: Group I: unpulsed DC pre-conditioning prior to vaccination #4; Group II: Td pre-conditioning prior to vaccination #4; or Group III: basiliximab infusions at vaccination #1 and #2 with Td pre-conditioning prior to vaccination #4. As of March 2017 (AMD 49), randomization of patients to Group III has been terminated. Please see Section 9.1.1 for a detailed outline of the randomization strategy for vaccine site pre-conditioning and Section 9.1.7 for a detailed description of the double blinding process. The study cycle of TMZ comprises a targeted dose of 150-200mg/m²/d for 5 days every 5 (± 1) weeks. All patients will receive up to a total of 10 DC vaccines given bilaterally at the groin site unless progression occurs. DC vaccines will be given i.d. and divided equally to both inguinal regions. DC vaccines #1-3 will be given every two weeks, thus delaying the initiation of TMZ cycle 2 for all patients. All remaining TMZ cycles will continue every 5 (± 1) weeks. Before the first DC vaccination, patients will receive 0.5 mL of Td (tetanus and diphtheria toxoids adsorbed) intramuscularly into the deltoid muscle to ensure adequate immunity to the tetanus antigen. The Td vaccine will be obtained through Duke Investigational Chemotherapy Services (ICS) Pharmacy. All patients will undergo leukapheresis again for immunologic monitoring with specific assessment of baseline antigen-specific cellular and humoral immune responses and further DC generations 4 ± 2 weeks after vaccine #3.

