
If the patient is determined to have progressive disease, the patient may be considered for eligibility on the INTERCEPT study (INTracerebral EGFR-vIII Chimeric Antigen Receptor Gene-Modified T Cells for PaTients with Recurrent GBM, Pro00083828). If the patient is determined to be eligible for the INTERCEPT study (Pro00083828), the cells extracted from leukapheresis while they were on this study, ELEVATE, will be used to create the CAR T cells for administration in the INTERCEPT study.

Group I Treatment Plan (DC Vaccinations with pre-conditioning with Unpulsed DCs prior to the 4th DC vaccine) Patients in Group I will receive 1 x 10⁶ autologous unpulsed DCs in saline administered to a single side of the groin, and 0.4 mLs of saline administered to the contralateral side one day prior to the fourth DC vaccine, which is always given bilaterally at the groin site. Patients will then receive ¹¹¹In-labeled DCs as the 4th vaccine to compare the effects of different

skin preparations on DC migration followed by SPECT/CT imaging immediately and at 1 and 2 days after injections.

Group II Treatment Plan (DC Vaccinations with pre-conditioning with Td prior to the 4th DC vaccine)

Patients in Group II will receive a single dose of Td toxoid (1 flocculation unit, Lf, in 0.4 mLs) administered to a single side of the groin, and 0.4 mLs of saline administered to the contralateral side one day prior to the fourth DC vaccine, which is always given bilaterally at the groin site. Patients will then receive ¹¹¹In-labeled DCs as the 4th vaccine to compare the effects of different skin preparations on DC migration followed by SPECT/CT imaging immediately and at 1 and 2 days after injection.

Group III Treatment Plan (DC Vaccinations with basiliximab infusions prior to 1st and 2nd DC vaccine with Td pre-conditioning prior to 4th DC vaccine)

Patients in Group III will receive the first 3 DC vaccines every 2 weeks same as Groups I and II only they will also receive basiliximab 20 mg I.V. 7 days before DC vaccine # 1 and 7 days before DC vaccine # 2. Prior to the 4th vaccine, patients will receive a single dose of Td toxoid (1 flocculation unit, Lf, in 0.4 mLs) administered to a single side of the groin, and 0.4 mLs of saline administered to the contralateral side one day prior to the fourth DC vaccine, which is always given bilaterally at the groin site. This group will not undergo migration studies.

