15.5.2 Other Primary Objective: Migration

Within Groups 1 and 2, the percentage of ¹¹¹In-labeled DCs reaching inguinal nodes at vaccination #4 is calculated from the initial signal at the injection site in the groin to 48 hours post-vaccination. A Wilcoxon rank-sum test will be used to compare assigned treatment groups (Groups I and II) with respect to migration. This analysis will be based upon the first 12 patients within each arm (Groups I and II) that receive vaccination #4.

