15.9.3 Other Primary Objective: Migration

One goal of this study is to validate observations made in the recently completed ATTAC trial concerning Td toxoid pre-conditioning. The design of this study (Groups I and II) is identical to

the ATTAC trial in that patients with newly diagnosed GBM underwent surgery followed first by SOC treatment (temozolomide + XRT) and then by 3 vaccinations. Prior to the 4th vaccination, patients were randomized to unpulsed DCs or Td tetanus pre-conditioning. The percentage of ¹¹¹In-labeled DCs reaching inguinal nodes was calculated from the initial signal at the injection site in the groin to 48 hours after the 4th vaccination.

In this study, the first 12 patients in Groups I and II will have their DCs labeled will undergo migrations studies to assess the migration objective.

A bootstrap approach was used to determine the sample size required for a comparison of migration rates using the Wilcoxon rank-sum test (also the Mann-Whitney U test) to have 95% power to detect a difference similar to that observed in the ATTAC study. Re-sampling with replacement from the pilot ATTAC study data was used in the 10,000 bootstrapping simulations.

With 12 patients in the Td toxoid arm (Group I) and 12 patients in the unpulsed DC arm (Group II) who have undergone migration studies at vaccination #4, simulations show that there is 95% power to detect the difference observed in the ATTAC trial assuming $\alpha=0.05$.

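### The migration objective claims a systemic effect, but Td goes in one groin and neither endpoint nor test says which side is measured, so a local effect could be reported as systemic

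*Combined protocol and SAP*

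**What the plan says.** **Objective.** Section 8, Table 1 lists as a primary objective whether "pre-conditioning of the vaccine site with Td toxoid systemically increases the migration" of the pp65 DCs to the inguinal nodes.

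**Intervention.** Under Section 9.1 the pre-conditioning agent (Td in Group II, unpulsed DCs in Group I) is "administered to a single side of the groin, and 0.4 mLs of saline administered to the contralateral side" the day before vaccine 4. Both groins then receive labelled cells: "DC vaccines will be given i.d. and divided equally to both inguinal regions".

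**Endpoint.** Table 1 defines one percentage of labelled DCs reaching the inguinal nodes, which "will be calculated from the initial signal at the injection site in the groin to 48 hours after the" fourth vaccination. Sections 15.5.2 and 15.9.3 describe the same quantity. None of the three gives a side or a rule for combining sides.

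**Analysis.** Section 15.5.2 names a single test: "A Wilcoxon rank-sum test will be used to compare assigned treatment groups (Groups I and II) with respect to migration". On the number of patients, it then says: "This analysis will be based upon the first 12 patients within each arm". Section 15.9.3 adds that "simulations show that there is 95% power to detect the difference observed in the ATTAC trial" at alpha 0.05, sidedness not stated.

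**Basis for the systemic claim.** Section 7.2 reports preclinical work in which migration rose equally in both groins whichever side received Td, "supporting a systemic response to recruit peripherally administered DCs". Section 9.2 reports a bilateral increase in the earlier randomised trial, which this study is meant to validate, and calls the saline side the control.

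**The concern.** A systemic effect of a one-sided injection is an effect on the side that was not injected. Sections 7.2 and 9.2 recognise this by resting the claim on a two-sided rise. That reasoning was not carried into the endpoint or the test.

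A local explanation is realistic on the plan's own account: Section 7.2 says Td inflames the intradermal site and so promotes migration of the cells injected there. Any patient value that includes the pre-conditioned groin can therefore differ between groups with no remote effect at all. No planned comparison isolates the saline side.

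More than wording is at stake. Section 15.1 says that, with enrolment closed, migration has enough subjects to be powered, while the survival comparisons may not be. A positive migration result is therefore likely to carry weight, and it could be read as confirming a systemic effect that the planned test cannot show.

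**Working it through.** **1. The plan's own figure.** The 95% power comes from resampling pilot data that the documents do not show, so it cannot be reproduced. It can be back-solved to the standardised shift it implies, using a normal approximation with Wilcoxon efficiency 3/π = 0.955:

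d = (z for alpha + z for power) × √(2 / (12 × 0.955))

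- Two-sided: (1.960 + 1.645) × 0.418 = 1.51
- One-sided: (1.645 + 1.645) × 0.418 = 1.37

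Simulated Wilcoxon tests on normal data (10,000 runs) give 1.62 and 1.44. The plan thus counts on a shift of roughly 1.4 to 1.6 SD, without saying of which side or combination.

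**2. What each reading of the endpoint can show.**

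| Value per patient | Can it separate local from systemic? |
|---|---|
| Pre-conditioned side only | No; local and remote effects are fully confounded |
| Sum or mean of both sides | No; see step 3 |
| Saline side only | Yes; it tests a remote effect of Td relative to unpulsed DCs |

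The documents do not choose among these.

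**3. Why a mean cannot separate them.** If Td shifts the pre-conditioned side by a and the saline side by b, the patient mean shifts by (a + b)/2. An effect of D on both sides gives (D + D)/2 = D. A local effect of 2D with nothing opposite gives (2D + 0)/2 = D. The shift is the same.

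Simulation with unit SD per side, within-patient correlation 0 to 0.8 (assumed), and D set so that the bilateral case has 95% power:

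| True effect | Mean of sides significant | Saline side significant |
|---|---|---|
| D on both sides | about 95% | 72–93% two-sided, 75–93% one-sided |
| D, local only | 43–44% two-sided, about 51% one-sided | 4–5% |
| 2D, local only | about 95% | 4–5% |

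**4. The same question on the percentage scale.** Assumptions: log-normal side-specific percentages with median 3% (Section 7.3 says generally under 5% of cells arrive), correlation 0.5 on the log scale, sides averaged, 12 per arm, two-sided 0.05, 4,000 trials per cell. Spread, correlation, fold effect and averaging are all assumed. The fold effect is Td's local excess over unpulsed DCs. Share of trials significant on the average when Td acts only locally:

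| Local effect | log-SD 0.4 | log-SD 0.6 | log-SD 0.8 |
|---|---|---|---|
| 1.5-fold | 30% | 16% | 11% |
| 2-fold | 73% | 39% | 24% |
| 3-fold | 99% | 82% | 57% |

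At log-SD 1.0 the 1.5-fold figure is about 9%. The saline-side test stays at about 3% to 5% throughout, its nominal level.

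**5. Price of the saline-side test.** With a true 2-fold effect on both sides, its power in this model is about 97%, 73% and 51% at log-SD 0.4, 0.6 and 0.8, against 99%, 85% and 63% for the average.

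Section 15.9.3 attaches the Td label to Group I; group assignments here follow Section 9.1.

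**The case against.** Four points deserve weight.

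- **Pooling is not stated.** A reader might infer that the plan averages the sides and so *would* report a local effect as systemic. The documents do not support that. They are silent on combination, Section 7.2 speaks of injection sites and regions of interest in the plural, and the imaging procedure it cites is not included. This stands: the defect is undefined handling of the sides. But an imaging procedure that records each side would supply data, not a pre-specified comparison.
- **The planned test is not wrong in itself.** Sections 15.1, 15.5 and 15.9.3 speak of migration without *systemically*, and Section 15.5 frames the contrast as Td against unpulsed DCs. For that question the Wilcoxon test is valid, and deleting one word from Table 1 would also remove the mismatch. This stands, and the fix allows for it. Yet Sections 7.2, 7.3 and 9.2 show that the systemic claim is central to the rationale.
- **The comparator is active.** Section 9.2 says unpulsed DCs were chosen because prior DC injection increased migration. Td's local excess over them could be small, which is why the illustration runs down to about 10%.
- **Moving the primary test has costs.** Replacing it could depart from the quantity behind the 95% power and from the trial being validated. Hence the saline-side test should be added beside the existing one, not substituted for it.

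**Conclusion.** The point holds in this form: objective and analysis do not match, because the objective claims a systemic effect, side is undefined, and no planned test isolates the saline side. Unless the unstated measure is the saline side alone, a significant result cannot distinguish a local effect of Td relative to unpulsed DCs from a systemic one, and could be reported as the latter.

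That conclusion rests on the wording and the algebra in step 3, not on the simulations. The range of about 10% to 99% shows only that the risk may be small or near certain depending on inputs the documents do not give. It should not be read as an estimated rate of false systemic claims. Nor is the Group I against Group II test invalid for a difference in migration.

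**What to change.** 1. In Table 1 and Section 15.5.2, compute the percentage separately for each groin: node signal at 48 hours over that side's initial injection-site signal.
2. State how the two sides are combined for the existing Wilcoxon test, consistent with the quantity resampled to obtain 95% power in Section 15.9.3.
3. Add a pre-specified Wilcoxon comparison of the saline-side percentage, Group II against Group I, as the evidence required for *systemically*. Give it its own power statement by re-running the bootstrap on the earlier trial's contralateral values, if they exist.
4. If that comparison is not adopted or does not support the claim, limit the conclusion to an increase in migration. If it is not adopted, also delete *systemically* from the objective.

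**Cost.** Protocol and SAP wording, plus per-side regions of interest on scans already planned. The saline-side test may have less than 95% power with 12 per arm. Because enrolment has closed (Section 15.1) and the statisticians are unblinded (Section 9.1.7), the date of the change relative to any look at migration data should be recorded so that the added test is not taken for a post hoc choice.
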